We will conduct a three-group, between-subjects experiment to compare varying cigarillo warning formats: Surgeon General text-only, FDA-proposed text-only, and our developed pictorial cigarillo warning labels. This will be a single survey study.

Setting

Survey participants will complete the online survey in a location of their choosing.

Subjects Selection Criteria

Participants will be recruited by Kantar, a leading data and consulting company with access to 21 million respondents in the United States. Kantar has participated in survey programming and data collection for various social science and public health studies, including tobacco. They will recruit a total of 1,575 cigarillo users, including oversampling Black/African American cigarillo users, with an estimated total of 635 Black/African American and 647 White cigarillo users

Inclusion Criteria

- Age 21-35
- Current cigarillo users: used cigarillos at least one time per week in the past month
- Members of the Kantar Media panel

Exclusion Criteria

- Non-English speakers
- Non-current cigarillo users
- Not members of Kantar Media

Sample Size

- We estimate 1575 participants will be eligible to complete the survey.

Interventions and Interactions

Kantar will contact individuals to participate, who will complete an eligibility screener. Eligible participants will first complete measures of demographics and tobacco use behaviors. Next, participants will be randomized to one of three experimental conditions to complete six purchasing tasks (i.e., mock shopping trips). Participants will indicate their preferred brand and flavor of cigarillos.³² If their preferred brand of cigarillo is not one of the top four brands, we will ask them to select one of the available brands. The experimental stimuli will be placed on that branded packaging.

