In secondary analyses, demand curves will be generated for each cigarillo warning condition in each of the ETM conditions using the exponential demand equation, $Q = Q_0 * 10^k(e^{-\alpha Q_0 C} - 1)$, where Q is the mg of nicotine purchased at a given price, Q_0 is peak demand consumption or intensity (typically occurring at the lowest price), k is a constant across all compared conditions, and alpha (α) is the rate of change in demand or elasticity.³⁵ To determine the extent to which pictorial warnings decrease cigarillo purchasing relative to the text-only warning conditions, the global fits of the demand curves for cigarillos from each condition will be compared using an extra-sum-of-squares F-test, which compares whether the fitted parameters (specifically, Q_0 and α) are significantly different across each curve. A significant difference in α would represent a difference in the essential value of the product, while a difference in Q_0 would indicate that purchasing was reduced in absolute terms but the underlying 'value' of the product was unchanged.^{36,37} Finally, each individual demand index will be compared across conditions using t-tests to determine if pictorial warnings affected specific indices of demand differentially. The number of cigarillos purchased is higher for text-only warnings compared to pictorial warnings at the same price, but demand overall will decrease as price increases.

Exploratory analyses will examine the effects of warning condition on other constructs in the conceptual model including negative affect, cognitive elaboration, behavioral intentions, and warning recall/recognition. Because these outcomes are measured only once after the completion of all six purchasing tasks, continuous outcomes will be modeled using standard linear regression modeling and categorical outcomes will be modeled using logistic and multinomial regression. All tests will be two-sided with a 0.05 significance level.

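### The demand-curve rule infers unchanged value from a Q0 difference, with no condition on alpha; at best it treats a non-significant alpha as proof of no change

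*Combined protocol and SAP*

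**What the plan says.** The rule is in the Analytic Plan, in the paragraph on secondary demand-curve analyses. Cigarillo demand curves are fitted by warning condition and compared with an extra-sum-of-squares F-test, which "compares whether the fitted parameters (specifically, Q_0 and α) are significantly different across each curve". One sentence then says how to read the result. Its first half is: "A significant difference in α would represent a difference in the essential value of the product". Its second half is: "while a difference in Q_0 would indicate that purchasing was reduced in absolute terms but the underlying 'value' of the product was unchanged". The words at issue are "the underlying 'value' of the product was unchanged". After that, "each individual demand index will be compared across conditions using t-tests". The next paragraph adds: "All tests will be two-sided with a 0.05 significance level".

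The documents give no equivalence margin for alpha, do not require an interval for it, and do not say how to read a result in which both parameters differ.

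**The concern.** Q0 and alpha are separate parameters of the curve: intensity at the lowest price, and the rate at which demand falls as price rises. The plan assigns essential value to alpha. Whether value changed is therefore a question about alpha, and a difference in Q0 does not answer it. The second half of the sentence nevertheless draws a conclusion about value from Q0.

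The background section says that warnings may work by reducing a product's value, and that the study is meant to inform rulemaking. If pictorial warnings lower both intensity and value, but the alpha test misses, the rule as written leads to a report that value did not change. That would understate the warnings' effect on a construct the protocol itself puts forward.

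**Working it through.** The plan states no power, SD, effect size or margin for Q0 or alpha, so there is no figure of its own to reproduce. The main check is logical; the numbers only show scale.

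**1. The four possible results under the rule**

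| Q0 | alpha | Alpha clause says | Q0 clause says |
|---|---|---|---|
| no difference | no difference | silent | silent |
| no difference | differs | value differs | silent |
| differs | no significant difference | silent | value unchanged |
| differs | differs | value differs | value unchanged |

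In row 4 the two clauses, read literally, disagree. If the sentence is read as a contrast (Q0 differs *but alpha does not*), row 4 is settled by the alpha clause. Row 3 is the same on either reading: the only support for 'unchanged' is a failure to reject equality of alpha.

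**2. How often a real alpha shift would be missed (illustration)**

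Inputs from the documents: 1,575 participants (Subjects Selection Criteria), three groups (Design), two-sided 0.05 (Analytic Plan). Assumed: equal allocation, since no ratio is stated; one log-alpha estimate per participant; a pairwise two-sample z-test.

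- Per arm: 1,575 / 3 = 525.
- Standard error of a difference in SD units: √(2/525) = 0.0617.
- Probability of non-significance for a true shift d: 1 − [Φ(d/0.0617 − 1.96) + Φ(−d/0.0617 − 1.96)].

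| True alpha shift (SD) | d / SE | Non-significant |
|---|---|---|
| 0.05 | 0.81 | about 87% |
| 0.10 | 1.62 | about 63% |
| 0.15 | 2.43 | about 32% |
| 0.20 | 3.24 | about 10% |
| 0.25 | 4.05 | about 2% |

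**3. What a null result leaves open**

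The 95% half-width is 1.96 × 0.0617 = 0.121 SD. With an assumed log-alpha SD of 1.0, an estimate of exactly no difference has an upper limit for the alpha ratio of exp(0.121) = 1.13. With SDs of 0.8 and 1.3 the limit is 1.10 and 1.17.

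**4. What an alpha ratio of 1.13 means for purchases**

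Use the plan's equation, Q = Q0 × 10^[k(e^(−αQ0C) − 1)], with assumed k = 2, Q0 = 20 and α = 0.004, against α = 0.004 × 1.13 = 0.00452. The percentage changes depend only on k, the product αQ0 (0.08) and the ratio. Prices are those in Interventions and Interactions.

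| Price | α = 0.004 | α = 0.00452 | Reduction |
|---|---|---|---|
| $0.25 | 18.26 | 18.04 | 1.2% |
| $0.50 | 16.70 | 16.32 | 2.3% |
| $0.75 | 15.29 | 14.79 | 3.3% |
| $1.50 | 11.88 | 11.15 | 6.1% |
| $3.00 | 7.49 | 6.70 | 10.5% |
| $6.00 | 3.46 | 2.91 | 15.8% |
| Total | 73.07 | 69.91 | 4.3% |

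**The case against.** **The sentence is a contrast, not two independent rules.** The natural reading of its linking word is that alpha change is set against Q0 change alone. On that reading alpha already governs when both differ, and there is no contradiction. This largely stands. A reader might infer that the plan contradicts itself outright, but the documents support that only if the Q0 clause is taken literally. What remains is that the both-differ case is not spelled out, and that the Q0-only case still rests on non-significance.

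**The reading is attributed to cited sources.** They may condition the Q0 statement on alpha. That cannot be checked here, and the plan's own text does not carry any such condition.

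**Alpha is tested directly, and nothing says its estimate will be withheld.** True, and this makes the remedy easy. It does not alter the conclusion the plan says it will draw.

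**The numbers do not model the planned test.** The sentence follows an F-test on condition-level fits, whereas the illustration uses participant-level two-sample tests, which are closer to the later t-tests. The F-test's error rates could differ. The miss rates are also ordinary type II error at assumed effect sizes. Both points stand: the figures show that a miss is plausible and do not estimate how often this trial would report wrongly.

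**The purchase effect looks large only at the top prices.** Quoting the 10% to 16% reductions at $3.00 and $6.00 alone would mislead. The four lower prices show 1% to 6%, and the protocol gives an average price of $0.91 per cigarillo. The six-trip total, 4.3%, is the fairer summary.

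**Conclusion.** The point holds as a fault in an interpretation rule. A Q0 difference cannot show that alpha, and hence value as the plan defines it, is unchanged. On the charitable reading the rule accepts the null from a non-significant test; on the literal reading it also conflicts with the alpha clause when both parameters differ. Neither conclusion needs a numerical assumption.

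The size is illustrative: alpha shifts of 0.10 and 0.15 SD missed in about 63% and 32% of trials, and an alpha ratio of 1.13 corresponding to 4.3% fewer purchases in total (1.2% to 15.8% by price). These rest on equal allocation, one log-alpha estimate per person, two-sample tests in place of the F-test, and assumed values of k, Q0, alpha and the log-alpha SD.

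A reader might also infer that a formal equivalence test is mandatory, or that the main result is at risk. The documents support neither. A margin matters only if the sponsor wishes to assert no change. The primary outcome, the number of cigarillos purchased, has its own model, and neither it nor the sample size depends on this rule.

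**What to change.** Replace the interpretive sentence with a rule that covers each result:

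1. Alpha alone governs statements about essential value.
2. If alpha and Q0 both differ, report a change in value and a change in intensity.
3. If only Q0 differs, report the change in intensity, give the alpha difference or ratio with its confidence interval, and state that a change in value was not shown.
4. Use 'unchanged' only if the sponsor prespecifies and justifies an equivalence margin for alpha and the interval lies within it. The documents offer no basis for any particular margin. If the sponsor does not want to make that claim, no margin is needed.

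The cost is a few sentences in the Analytic Plan and one reported interval, with no new data and no change to the sample size. The downside is that unchanged value can no longer be claimed from a non-significant test.

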The average total number of cigarillos purchased is the primary outcome.

We will assess secondary outcomes: average total amount (mg) of combusted and non-combusted tobacco purchased in the ETM.

In secondary analyses, we will also generate demand indices for cigarillos, including: demand intensity (consumption at the lowest cigarillo cost), demand elasticity (rate of change in demand for cigarillos), price of cigarillos resulting in maximum purchasing, the amount of money spent at the maximum purchasing price.

In exploratory analyses, we will assess cross-price elasticity measures, negative affect, cognitive elaboration (thinking about the warnings), intentions to quit using cigarillos, perceived message effectiveness, and warning recall/recognition, which is a measure of attention.

We will also measure several **covariates**: use of other tobacco products, cigarillo dependence, sexual orientation, race/ethnicity, socioeconomic status, sex, gender identity, and age.

Analytic Plan

This study will examine the impact of cigarillo warnings on purchasing behavior in a hypothetical shopping task using the online Experimental Tobacco Marketplace. The primary outcome is the average total amount of cigarillos “purchased” (hypothetical shopping task) compared across study conditions.

Baseline differences between participants (e.g., sex) across warning conditions will be examined using t-tests for continuous variables and χ^2 tests for categorical variables to evaluate randomization balance. The primary outcome, average total number of cigarillos purchased, will be modeled using random-effects linear regression models to account for the within-person correlation among the repeated measures represented by the six purchasing tasks. Warning condition will be included as a between-subjects fixed effect. Models will control for any variables that differ at baseline between conditions. We will also assess whether Black/African-American race moderates the effect of warning condition by including interaction terms between Black/African American race and warning condition. These same analyses will also be

conducted for our secondary outcomes for average total of mg combusted and non-combusted tobacco products.

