In exploratory analyses, to determine the extent to which each alternative product substituted for cigarillos, cross-price elasticities will be calculated as the slope of the regression line (B_1) fit to the log-transformed mean purchasing in mg of nicotine for each alternative tobacco product when offered at fixed prices (C) versus log-transformed cigarillo price (P): $\log C = B_0 + B_1 \log P$. Positive values indicate product substitution. We will use PRISM GraphPad Version 8.1.1 to generate the behavioral economics indices, demand curves, and cross-price elasticities. We will be able to determine if viewing a pictorial warning on a cigarillo resulted in substitution with another tobacco product without a pictorial warning, such as cigarettes or e-cigarettes, or a non-tobacco product, such as food or drink.

Every effort will be made to minimize the presence of missing data. Analyses will use all available data. Since missing data in a single item of a multi-item scale leads to a missing total, we will consider imputing both at the level of the item and scale total. Additionally, to evaluate the generalizability of our results, we will use t-tests and chi-squared tests to examine pairwise differences in characteristics between participants for whom we have complete data and those for whom we do not.

Human Subjects Protection

Subject Recruitment Methods

Kantar works with permission-based panels with 88 million respondents, including 21 million in the United States. Recruitment includes traditional advertising and through internal and external affiliate networks. Kantar uses a diverse set of sources to reduce panel bias. When recruiting participants into studies, Kantar engages in data validation to ensure quality respondents and

responses. Kantar will recruit participants, directly inviting them to participate in the experiment. Potential study participants will complete an eligibility screener for inclusion into the ETM study. Participants must be ages 21-34 and be current cigarillo users (use cigarillos at least one time per week for the past month). Further, because we are studying cigarillo warnings in the U.S., only those living in the U.S. are eligible. Kantar will also oversample for young adult Black/African American cigarillo users. Kantar oversamples by enrolling approximately 20% additional participants to the study.

Informed Consent

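### Elasticity and price at maximum purchasing are undefined for participants who buy no cigarillos at any price, so t-tests on these two indices compare only buyers, a group the warning itself can change

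*Combined protocol and SAP*

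**What the plan says.** The Outcome Measure section lists four cigarillo demand indices for secondary analysis: intensity (purchasing at the lowest price), "demand elasticity (rate of change in demand for cigarillos"), the price at which purchasing is at its maximum, and the money spent at that price.

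The Analytic Plan handles them in two steps. First, "demand curves will be generated for each cigarillo warning condition", and the fitted Q0 and alpha are compared between curves with an extra-sum-of-squares F-test. Then "each individual demand index will be compared across conditions using t-tests". On software: "We will use PRISM GraphPad Version 8.1.1 to generate the behavioral economics indices, demand curves, and cross-price elasticities".

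Under Interventions and Interactions, participants may buy any mix of tobacco and non-tobacco items within budget, so buying no cigarillos is a valid response. No section says how the indices are obtained for someone who buys none at all six prices. The missing-data paragraph keeps all available data, considers imputation for multi-item scales, and compares participants with and without complete data. A non-buyer has complete purchase data, so none of these provisions clearly applies.

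**The concern.** An ordinary t-test between conditions needs replicate values within each condition. If those values are elasticities fitted person by person, a participant with six zeros has none to contribute and drops out of the test. The same holds for the price at maximum purchasing.

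The people lost may include those whom a warning deterred completely. Being in the analysed set is then an outcome of the randomised warning, and the comparison is no longer between randomised groups. This matters for interpretation because the plan reads a difference in alpha as a difference in the essential value of cigarillos. If pictorial warnings turn the most price-sensitive users into non-buyers, the remaining pictorial buyers look less elastic than they should. A real increase in elasticity could be masked, or a difference could appear where none exists.

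**Working it through.** **Inputs from the plan.** Sample: "They will recruit a total of 1,575 cigarillo users". Design: "We will conduct a three-group, between-subjects experiment". Allocation: "participants will be randomized to one of three experimental conditions", with no ratio given. Level: "All tests will be two-sided with a 0.05 significance level". Prices: \$0.25, \$0.50, \$0.75, \$1.50, \$3.00 and \$6.00. The plan gives no power, effect size, SD or non-buyer rate, so there is no figure of its own to reproduce.

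**Assumptions.** Equal allocation, 1,575 / 3 = 525 per arm. Non-buyers 5% in a text-only arm and 10% or 15% in the pictorial arm. Log alpha normal with SD 1. Non-buying driven by a latent liability with correlation rho to log alpha, so that for rho above 0 the more elastic people tend to stop buying.

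**Step 1: can alpha be estimated from six zeros?** The equation is Q = Q0 × 10^(k(exp(−alpha × Q0 × C) − 1)). Alpha enters only through the product alpha × Q0 × C. At Q0 = 0 the predicted Q is 0 at every price whatever alpha is. The squared error against six zeros was exactly 0 for each alpha tried, from 0.0001 to 1. Numerical fits (k = 2 assumed, alpha bounded at 1,000) ended with Q0 near 0 and alpha between about 976 and 991, with a variance in the millions. Such an alpha reflects the bound, not the data.

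**Step 2: which indices are affected?**

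| Index | Value for a non-buyer |
|---|---|
| Intensity, as observed | 0 |
| Maximum spending, as observed | 0 |
| Elasticity (alpha) | not estimable |
| Price at maximum purchasing | undefined (six-way tie at 0) |

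**Step 3: bias when the warning has no effect on alpha.** With a proportion p of non-buyers removed, the mean log alpha among buyers is −rho × φ(c) / (1 − p), where c is the (1 − p) standard normal quantile.

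- p = 5%: 0.1031 / 0.95 = 0.1086
- p = 10%: 0.1755 / 0.90 = 0.1950
- p = 15%: 0.2332 / 0.85 = 0.2743

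The bias (pictorial minus text) is −rho × 0.0864 for 5% v 10%, and −rho × 0.1657 for 5% v 15%. Rejection rates come from simulated two-sample t-tests at two-sided 0.05.

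| rho | Bias, 5% v 10% | False positives | Bias, 5% v 15% | False positives |
|---|---|---|---|---|
| 0 | 0 | about 5% | 0 | about 5% |
| 0.3 | −0.026 SD | about 7% | −0.050 SD | about 12% |
| 0.7 | −0.060 SD | about 17% | −0.116 SD | about 47% |

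Repeat runs of the last cell gave 47% to 50%. With equal rates (5% v 5%) the bias is 0 and rejection about 5% at every rho tried.

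**Step 4: scale.** The standard error of a difference is √(2/525) = 0.0617 SD, so 525 per arm detects (1.960 + 0.842) × 0.0617 = 0.17 SD with 80% power. At rho = 0.7 a true difference of 0.20 SD would be estimated as 0.20 − 0.06 = 0.14 SD (5% v 10%) or 0.20 − 0.12 = 0.08 SD (5% v 15%).

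**Step 5: why zeros should stay in the other two indices.** In an assumed example (median intensity 10, log-SD 0.8, correlation 0.6 between non-buying and lower intensity, non-buyers 5% v 15%), the pictorial-minus-text difference in mean intensity is −0.65 with zeros kept and +0.91 with non-buyers dropped. Dropping them reverses the sign.

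**The case against.** The best reply is that the plan describes curves only at condition level. The phrase about individual indices may mean each index in turn, not each person's index, and a t-statistic can be formed from condition-level estimates and their standard errors. On that reading nobody is excluded. This has some force, since the level of fitting is never stated. But the t-tests follow a separate condition-level F-test on Q0 and alpha, and for those parameters they would largely repeat it. Participant-level values remain the more natural reading.

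Several further points stand:

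- The F-test can keep non-buyers, because the equation models Q and not its logarithm. The primary random-effects model can also keep them.
- Total non-buying may be rare. Entrants use cigarillos at least weekly, receive their usual weekly tobacco budget, and start at \$0.25 against an average price of \$0.91 given in the plan.
- Buying nothing even at \$0.25 is most directly a result about Q0, so a strong link with alpha cannot be presumed.
- A mixed-effects model does not identify a non-buyer's alpha; it handles such people through distributional assumptions.

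A reader might infer that all four indices must lose non-buyers. The documents do not support that: intensity is defined as purchasing at the lowest price, which is observed as 0, and maximum spending is likewise 0.

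**Conclusion.** The point holds for two of the four indices. On the natural reading of the t-test step, elasticity and price at maximum purchasing are compared among buyers only, a subset formed after randomisation that the warning can alter. This follows from the stated equation and test, and no provision in the plan covers it.

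A reader might go further and conclude that the elasticity comparison is certainly biased, or that the main result is affected. Neither follows. Bias needs both unequal non-buyer rates and a link between non-buying and elasticity, and the documents give neither. Under the assumptions above it runs from 0 to about −0.12 SD, and false positives from the nominal 5% to about 47%; no single figure can be defended. Even at zero bias, the two tests describe buyers and not everyone randomised. The primary analysis is not affected. The change is worth making because these are prespecified secondary comparisons and the elasticity result carries a substantive interpretation.

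**What to change.** Amend the secondary demand analysis in the Analytic Plan:

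1. State the level at which the indices are derived. Compare intensity and maximum spending on observed values, with 0 for non-buyers.
2. Report and compare by arm the proportion who buy no cigarillos at any price. This is informative about deterrence in its own right.
3. For elasticity, replace the t-test on individually fitted alpha with a condition effect on Q0 and alpha in one mixed-effects (or two-part) demand model, fitted to all randomised participants with zeros included. State that it relies on distributional assumptions for non-buyers.
4. Label any buyers-only comparison of alpha or of price at maximum purchasing as conditional on buying.

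The cost is a change of wording, a little more analysis work, possible convergence effort, and a model fitted outside the software the plan names. No new data are needed.

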We will ask participants the average amount of money they spend each week on tobacco products; they will receive that balance for each mock (i.e., hypothetical) shopping trip, as is standard for ETM studies.³³ We will ask participants to imagine they were shopping in a convenience store, and to view six items available for purchase: preferred cigarillo brand, cigarette product (menthol and non-menthol), e-cigarette product (three variations), oral nicotine pouches, non-alcoholic drink, and snack food. They will be instructed to make hypothetical purchases of tobacco products that they would use for the week. In each shopping trip, the price of cigarillos will increase while those of alternative products remain the same. In each trial, participants can choose any combination of tobacco and non-tobacco products to ‘buy’, as long as they stay within their experimental budget. Across six mock shopping trips, the price of one of their preferred cigarillo products will increase from \$0.25, 0.50, \$0.75, \$1.50, \$3.00, \$6.00, based on an average price of \$0.91 per cigarillo.³⁴ Cigarette price will remain constant at \$6.00 per pack (\$0.30 per cigarette), e-cigarettes will be priced at \$4 per e-liquid pod or \$6 for 30 ml e-

liquid or \$12 for disposable device, and oral nicotine will be priced at \$4.00. Food and drink will be priced at \$2 each. Cigarillos will be purchased as singles to generate demand curves (see Measures and Analysis Plan).. This models other ETM studies.³³

After completing the hypothetical purchase tasks, we will assess additional constructs from our conceptual model. First, we will assess cigarillo warning label recognition (a measure of attention). We will then show the cigarillo warning to participants from their assigned experimental condition and ask them to respond to items assessing negative affect, thinking about the warnings, and intentions to quit using cigarillos.

At the end of this experiment, participants will view a **debriefing** page, including an explanation of the purpose of the study, emphasizing that the study is not promoting the use of cigarillos or any tobacco product and will include links to cessation services and information about the harms of cigarillo use. Participants will be compensated with 100 points (~\$2 value) by Kantar. These points can be used in exchange for a variety of items, including gift cards. We will not collect any identifying information such as name or birthdate.

Outcome Measure

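### The exploratory cross-price slopes are read by their sign, with no standard error, interval or test, so sampling noise can be reported as substitution

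*Combined protocol and SAP*

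**What the plan says.** The Analytic Plan sets out "to determine the extent to which each alternative product substituted for cigarillos, cross-price elasticities will be calculated as the slope of the regression line". The line is "fit to the log-transformed mean purchasing in mg of nicotine for each alternative tobacco product", regressed on log cigarillo price. The sentence after the equation is "Positive values indicate product substitution". The plan says nothing more on how B1 is to be judged.

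The data behind the line are described under Interventions and Interactions. "In each shopping trip, the price of cigarillos will increase while those of alternative products remain the same", and there are six trips, priced at $0.25, $0.50, $0.75, $1.50, $3.00 and $6.00. Each product therefore contributes six points. Besides cigarillos, the tobacco on sale is "cigarette product (menthol and non-menthol), e-cigarette product (three variations), oral nicotine pouches"; a drink and a snack complete the list, which the plan counts as six items.

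The general statement on testing is "All tests will be two-sided with a 0.05 significance level". It sets a level for tests that are named elsewhere. No test of B1 is named.

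**The concern.** Averaging over participants before fitting leaves six numbers per product and discards the information on how precisely each was measured. Those means carry sampling error, so the fitted slope will almost never be exactly zero even when purchasing of that product does not respond to cigarillo price. A reader given only a slope and its sign cannot tell a real response from noise.

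At stake is the statement the analysis exists to support, namely which products people move to as cigarillos become dearer. The Background presents the study as evidence for rulemaking, and the Analytic Plan says it will be able to determine substitution. A list of substitutes drawn up from signs alone would be partly chance.

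**Working it through.** **Inputs.** From Interventions and Interactions: six cigarillo prices, with the prices of alternatives held constant. From the Analytic Plan: the line is fitted to log mean purchases. From Subjects Selection Criteria and Design: 1,575 participants in three groups. That is 1,575 / 3 = 525 per group if allocation is equal, which is an assumption because no ratio is stated. The plan gives no error rate or precision for B1, so there is no figure of its own to reproduce.

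**Step 1: one product with no relation to price.** With x = log10 price, the estimate is B1 = Σ(x − x̄)·log C / Σ(x − x̄)², and Σ(x − x̄)² = 1.306 for the six prices. If the true slope is zero and the error is symmetric, P(B1 > 0) = 0.50. Simulation on these prices gave 0.499 to 0.501 with independent, exchangeable or serially correlated normal errors. It gave 0.49 to 0.52 with skewed purchases containing many zeros, at 525 or 1,575 people. Sample size does not enter. A weak true complement, with a slope one standard error below zero, still comes out positive with probability Φ(−1) = 16%.

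**Step 2: several products.** Six items less cigarillos, drink and snack leaves three alternative tobacco products. If none is related to price:
- independent slopes: 1 − 0.5³ = 87.5%
- slopes correlated at 0.3 (assumed): 1 − [1/8 + (3/4π)·arcsin 0.3] = 1 − [0.125 + 0.2387 × 0.3047] = 1 − 0.198 = 80%

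These are the chances that at least one has a positive slope.

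**Step 3: would the standard error from the six-point fit be enough?** Six points less two parameters leaves 4 degrees of freedom and a critical t of 2.78. Requiring a two-sided 0.05 test to exclude zero, the chance of a false positive slope (nominal 2.5%) was:

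| Errors across the six means | False substitute |
|---|---|
| Independent or exchangeable | 2.5% |
| Serial correlation 0.5 | 7.5% |
| Serial correlation 0.9 | 15.4% |

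The test holds its level in the simple cases. It fails if adjacent trips are more alike than distant ones, which is plausible when the same people shop at steadily rising prices. It also loses power. With a true slope of 3 standard errors and independent errors it finds a positive slope 62% of the time, against Φ(3 − 1.96) = 85% if the standard error were well estimated from participants. Any bend in the true log-log relation enters the residual and widens the interval further.

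**Step 4: how large a slope can noise produce?** This needs figures the documents do not give. Assuming 10% to 40% of participants buy the product on a trip and latent within-person correlation is 0.5 to 0.8, simulated standard errors of B1 ran from 0.007 to 0.059. The low end is all 1,575 with purchases coded as bought or not; the high end is one group of 525. Then 1.96 × 0.007 = 0.014 and 1.96 × 0.059 = 0.116. The price range is 6.00 / 0.25 = 24-fold, so these slopes mean a rise in purchasing of 24^0.014 = 1.05 to 24^0.116 = 1.45 times from the lowest price to the highest.

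**The case against.** The strongest reply is that the sentence on positive values explains what the sign of a coefficient means and is not a classification rule. It directly follows the equation, and the stated aim is the extent of substitution, which is a magnitude. That reading is fair. A reader might infer that the plan commits itself to declaring substitutes by sign with a 50% error rate, but the text does not say so. The 50% applies only if the sign is used alone, and it is what any symmetric estimate gives at an exact null. What stands is that, on the gentler reading, the plan has no criterion at all for separating substitution from noise.

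A reader might also count the menthol, non-menthol and e-cigarette variants as six products, which gives 98% if independent (1 − 0.5⁶) or 92% at correlation 0.3. The store list does not support that count, because it totals six items only if each variant group is one item. Those figures would apply only if every variant were analysed separately.

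The step 4 standard errors rest on assumed purchase rates and correlations, and at the low end the false slope is negligible on its face. Both remarks are right; the high end is not negligible, and no minimum size is set.

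Finally, the analysis is labelled exploratory. That lowers the severity but does not remove the need for an interval.

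**Conclusion.** The point holds as a minor one. The plan attaches no uncertainty to B1 and offers only its sign as a guide, and the general 0.05 statement does not supply a test. If the sign is used alone, an unrelated product is read as a substitute 50% of the time, and at least one of three unrelated products 80% to 88% of the time. These figures assume true slopes of exactly zero and, for three products, a correlation between slopes of 0 to 0.3. The shared weekly budget makes exact zeros and independence approximations.

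Nothing here touches the primary outcome, the secondary outcomes or the sample size. A reader should not infer that the study's main comparison of warning formats is compromised. Whether a pictorial warning itself causes substitution is a further question, which needs a comparison of slopes between conditions and is not settled by this point.

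**What to change.** Keep the log-mean slope and add its uncertainty. Resample participants with replacement, keeping each person's six trips together, recompute the six means, refit the slope, and take a 95% interval from the resampled slopes. A log-link GEE on log price, clustered on participant, is an alternative. It weights the prices differently, so its slope may differ somewhat if the relation is curved.

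Suggested wording for the Analytic Plan: *B1 will be reported for each alternative product with a 95% confidence interval from a bootstrap over participants. A product will be described as a substitute only if the interval lies above zero and as a complement only if it lies below zero; otherwise we will state that no relation was shown.*

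With intervals that hold their level, the chance of a false substitute falls to 2.5% per product, and to 1 − 0.975³ = 7.3% for at least one of three independent ones.

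The cost is one or two sentences and a short script outside the named curve-fitting software. No new data or participants are needed. The small downside is that fewer products will be labelled substitutes.
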